
Safety Evaluate the safety and tolerability of repeated-dose administration of ALXN1840 15 mg/day and 30 mg/day in participants with WD
	
Safety parameters:
 
 • Treatment emergent adverse events (TEAEs)/serious adverse events (SAEs) • Clinical laboratory assessments (serum chemistry, hematology, coagulation, and urinalysis) • Physical examinations • Heart rate, intervals (PR, QRS, QT and QTc), and clinically significant electrocardiogram (ECG) findings as determined by triplicate 12-lead ECG • Vital sign assessments (blood pressure and heart rate)

Exploratory Determine dose response of ALXN1840 15 mg/day and 30 mg/day for copper balance in participants with WD
	Assess dose response of ALXN1840 on copper balance focusing on copper balance
Determine the effect of treatment duration on copper balance in participants with WD	Determine the effect of time following initiation of ALXN1840 treatment on copper balance
Assess the effects of ALXN1840 on ceruloplasmin, ceruloplasmin-bound copper, LBC profiles in plasma in participants with WD	Ceruloplasmin, ceruloplasmin-bound copper, and LBC: Change in ceruloplasmin at Days 1, 8, 25, 29, 36, and Day 39 compared with predose

Objectives	Endpoints
Assess dose proportionality at steady state of doses of ALXN1840 15 mg/day and 30 mg/day in participants with WD	Based on PK parameters
Assess effects ALXN1840 on copper:molybdenum ratio in plasma at steady state in participants with WD	Measure plasma copper:molybdenum ratios at steady state compared with predose
Assess the effects of repeat-dose ALXN1840 on copper:molybdenum ratio in urine and feces in participants with WD	Mean daily copper:molybdenum ratio in urine and feces at steady state compared with predose baseline

Note: The accumulation period refers to time from initiation of ALXN1840 (Day 1) to expected steady state at Day 10, based on 5 times the half-life of 2 days.

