7.4.3. Pharmacokinetic Parameter Analyses

The following plasma PK parameters, as data permit, will be calculated for total molybdenum and PUF molybdenum (as surrogate measures of ALXN1840 PK) after dosing on Days 1, 25, 29 and 39 using noncompartmental methods with Phoenix® WinNonlin® (Certara USA Inc., Princeton, New Jersey) Version 8.0 or higher or SAS Version 9.4 or higher (SAS Institute Inc., Cary, North Carolina), as applicable. Calculations will be based on the individual actual sampling times relative to the actual ALXN1840 reference dosing times recorded during the study.

- Time delay between the time of dosing and time of appearance of molybdenum concentration (T_{lag}) in plasma
- Maximum observed concentration (C_{max})
- Dose-normalized C_{max} (C_{max_n}); n = dose normalized
- Time to maximum concentration (T_{max})
- Trough (pre-dose) concentration observed at the start of the dosing interval (C_{trough})
- Time of last quantifiable concentration (T_{last})
- Observed concentration at the end of the dosing interval (C_{τ} , where $\tau = 24$ h)
- Area under the plasma concentration versus time curve (AUC) from time 0 to the last quantifiable concentration (AUC_t)
- Dose-normalized AUC_{t_n} (AUC_{t_n}); n = dose normalized
- AUC from time 0 to infinity (AUC_{∞}) (Day 1 only)
- Dose-normalized AUC_{∞} (AUC_{∞_n}); n = dose normalized
- AUC over the dosing interval (AUC_{τ})
- Accumulation ratio (AR) calculated as C_{max} , C_{trough} , and AUC_{τ} after repeat dosing divided by those after initial dosing on Day 1:

For 15 mg/day:

- $C_{max,Day25}/C_{max,Day1}$
- $C_{trough,Day26}/C_{trough,Day2}$
- $AUC_{\tau,Day25}/AUC_{\tau,Day1}$

For 30 mg/day:

- $C_{max,Day39}/C_{max,Day29,adjusted}$
- $C_{trough,Day40}/C_{trough,Day30,adjusted}$
- $AUC_{\tau,Day39}/AUC_{\tau,Day29,adjusted}$

Note: total molybdenum and PUF molybdenum concentration-time profiles on Day 28 after the last 15 mg ALXN1840 dose will be extrapolated to Day 29 (0-24 hr) and subtracted from the

observed Day 29 concentration-time profiles after the first 30 mg ALXN1840 dose for the estimation of the $C_{\max, \text{Day}29, \text{adjusted}}$, $C_{\text{trough}, \text{Day}30, \text{adjusted}}$, and $AUC_{\tau, \text{Day}29, \text{adjusted}}$.

- Apparent terminal phase elimination rate constant (λ_z)
- Terminal elimination half-life ($t_{1/2}$)
- Apparent total body clearance (CL/F) of ALXN1840 from plasma
- Apparent volume of distribution (V_d/F)

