For ALXN1840, equivalent molybdenum dose will be used to calculate total molybdenum CL/F and V_d/F values as described in Section 7.2.2. For ALXN1840 30 mg equivalent molybdenum dose is 6.66 mg.

Additional plasma PK parameters may be calculated if deemed appropriate.

For the PK analysis, values below the limit of quantification (BLQ) prior to the first measurable concentration will be set to zero whereas the rest of all other BLQ values will be treated as missing.

Pharmacokinetic parameters derived from plasma concentrations of total molybdenum and PUF molybdenum will be presented in data listings and summarized by analyte, treatment (dose), and day using the following descriptive statistics: number of participants, arithmetic mean, SD, arithmetic CV, GM, GMCV, 95% CI, median, minimum, and maximum. Geometric mean and geometric CV will be presented for C_{\max} and AUCs only. When calculating the geometric mean, values of 0 will be discarded.

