7.4.5. Pharmacokinetic Statistical Analyses

Attainment of steady state will be evaluated using stepwise testing for linear trend.

Plasma total molybdenum and total copper AUC_{tau} relationship will be assessed using linear least squares regression and E_{max} model.

If data permit, dose-proportionality for ALXN1840 will be assessed graphically and by using a power model (Smith, 2000; Newlands, 2006; EMA, 2010). The following PK parameters obtained on Days 25 and 39 will be assessed for dose proportionality: C_{max_n} and AUC_{t_n}. The log (PK parameters for plasma total and PUF molybdenum) will be included as a response variable and log (dose) will be included as a fixed effect in the power model:

$$\log(\text{PK Parameter}) = \mu + \beta * \log(\text{Dose}),$$

where $\beta = 1$ indicates perfect dose proportionality. Estimation of β , along with its 90% CI, will be provided.

Additional approaches to test dose proportionality, such as an ANOVA model, will be explored (Calvo, 2005).

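### SAP 7.4.5 assesses steady-state dose proportionality on AUC to the last quantifiable sample (AUC_t) rather than the 24 h AUCtau already derived, so a lost or off-time 24 h sample can shift the slope in either direction

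*SAP*

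**What the plan says.** Protocol section 3 lists an exploratory objective: "Assess dose proportionality at steady state of doses of ALXN1840 15 mg/day and 30 mg/day in participants with WD". SAP 7.4.5 implements it, data permitting, with a graph and a power model of log parameter on log dose, and reports the slope with a 90% CI. On the inputs it says: "The following PK parameters obtained on Days 25 and 39 will be assessed for dose proportionality". The two named are dose-normalised Cmax and dose-normalised AUC_t, for total and for PUF molybdenum. A slope of 1 is given as perfect proportionality.

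SAP 7.4.3 defines AUC_t as running "from time 0 to the last quantifiable concentration". It separately derives the "AUC over the dosing interval" (AUCtau, with tau = 24 h) and uses it for the accumulation ratios. SAP 7.4.5 itself uses AUCtau for the molybdenum-copper relationship. For values below the limit of quantification (BLQ), SAP 7.4.3 sets those before the first measurable concentration to zero, and "the rest of all other BLQ values will be treated as missing".

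**The concern.** Proportionality at steady state compares exposure over one dosing interval at two doses, so both areas should cover the same interval. AUC_t does not guarantee that. BLQ values after the first measurable one become missing, so the area stops at the last measured sample. Protocol Table 2 has no sample between 12 h and 24 h, so losing the 24 h value removes a large part of the interval at once. Parameters are computed from actual sampling times, so AUC_t also moves with the clock time of the last draw.

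If this happens at one dose and not the other, the difference in length is absorbed into the slope and read as a departure from proportionality. The SAP gives no reason for using the open-ended area here when it uses AUCtau elsewhere in the same section.

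**Working it through.** **Inputs from the documents.** Sampling at predose, 2, 4, 5, 6, 8, 12 and 24 h (Protocol Table 2). tau = 24 h (SAP 7.4.3). Total molybdenum half-life 24-51 h (Protocol 2.2). Doses 15 and 30 mg. About 10 participants (SAP 9.1).

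**Assumptions.** One-compartment linear kinetics, absorption rate 0.4-0.6/h, linear trapezoid (the SAP names no trapezoid rule), PUF half-life 4-12 h (not in the documents), and exact proportionality as the truth.

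**1. The plan's reference slope.** With two doses and all participants contributing at both, slope = [mean ln P(30) - mean ln P(15)] / ln(30/15).
- Unnormalised P: ln 2 / ln 2 = 1, the value the SAP states.
- Dose-normalised P, as the SAP names: ln 1 / ln 2 = 0.

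The stated reference of 1 is therefore reproduced only for unnormalised parameters. The shifts below are relative to whichever null applies.

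**2. Agreement case.** If the 24 h sample is quantifiable and drawn at 24 h at both doses, AUC_t = AUCtau and the shift is 0.

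**3. Shift from a shortened area.** Let f = AUC(0-12)/AUC(0-24). If a fraction p of participants is cut at 15 mg only, shift = +p × (-ln f)/ln 2. If the cut is at 30 mg only, the sign reverses.

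| Analyte | Half-life | Absorption rate | f | Shift, all affected | Shift, 1 in 10 |
|---|---|---|---|---|---|
| Total Mo | 24 h | 0.6/h | 0.560 | 0.84 | 0.08 |
| Total Mo | 51 h | 0.4/h | 0.524 | 0.93 | 0.09 |
| PUF Mo (assumed) | 4 h | 0.6/h | 0.797 | 0.33 | 0.03 |
| PUF Mo (assumed) | 12 h | 0.4/h | 0.601 | 0.735 | 0.07 |

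Worked line: -ln 0.560 / ln 2 = 0.580/0.693 = 0.84; divided by 10, 0.08.

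**4. Can the 24 h sample be BLQ for total molybdenum?** At steady state C24/Cmax is about 0.6 (half-life 24 h) to 0.8 (51 h). The steady-state trough is about 1.2-3.0 times the Day 1 Cmax. A quantification limit high enough to lose the Day 25 24 h sample would therefore make the whole 15 mg Day 1 profile unquantifiable. BLQ loss is implausible for this analyte. What remains is a sample missing for another reason.

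**5. Can it be BLQ for PUF molybdenum?** With half-life 6-12 h, loss at 15 mg needs a quantification limit above roughly 15-35% of the 15 mg Cmax. The documents give no limit to compare with that. A cut at 15 mg alone needs the limit to lie between C24 at 15 mg and C24 at 30 mg, a two-fold window. If both doses stop at the same sample, the slope returns to its null.

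**6. Off-time samples.** Protocol 8.5 tolerates 10% or 30 min, whichever is less; the Table 2 note allows ±10%. For total molybdenum, a last sample 30 min off on one day in all participants changes AUC_t by about 1.5-2% and the slope by 0.02-0.03 (for example ln 1.018 / ln 2 = 0.026). At 26.4 h (24 h + 10%) the shift is 0.10-0.12 if all are affected.

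**The case against.** The strongest reply is that the profile is designed to end at tau. Protocol Table 2 places the hour-24 sample just before the next dose, participants are inpatient until Day 40, and the same draws supply the Day 26 and Day 40 troughs needed for the accumulation ratios. In the expected case AUC_t and AUCtau are the same number and the change does nothing. That stands, and it is why the point is minor.

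A reader might infer that samples at 15 mg will be lost earlier and that this pushes the slope above 1. The documents do not support that, for four reasons.
- Nothing in them shows differential loss. For total molybdenum BLQ loss is implausible, and a sample missing for another reason has no preferred direction.
- For PUF molybdenum the case rests on a half-life and a quantification limit that are not given. Protocol 4.2 says PUF molybdenum includes molybdate from food. That background makes late BLQ values less likely and pulls the unnormalised slope down: if it is a share s of the 15 mg AUC, the slope is log2(2 - s), or 0.96, 0.93 and 0.85 for s = 5%, 10% and 20%.
- The 0.33-0.74 range needs every participant cut at 15 mg and none at 30 mg. The linear trapezoid across the 12-24 h gap also enlarges it: at half-life 4 h and absorption 0.6/h, exact integration gives about 0.24 rather than 0.33.
- The named parameter is dose-normalised, so its null slope is 0. A shift of 0.03-0.74 from there does not exceed 1.

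It can also be said that unequal end times would be visible, because T_last is derived and PK parameters are listed and summarised by analyte, dose and day. That would reveal the problem but not remove it from the slope. The dietary background is a separate bias and does not justify an area with a variable end.

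**Conclusion.** The choice of AUC_t is certain from the text; its effect is conditional. AUC_t is the less suitable area for a steady-state comparison, and it diverges from AUCtau only when the 24 h sample is missing, BLQ or off-time.

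For total molybdenum, one missing 24 h sample among 10 moves the slope by about 0.08-0.09, up if it belongs to Day 25 and down if to Day 39. For PUF molybdenum, with 15 mg alone cut at 12 h, the shift is about 0.03-0.07 for one in 10 and 0.33-0.74 for all, under an assumed half-life of 4-12 h. How often this would occur cannot be judged from the documents.

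These figures rest on linear one-compartment kinetics, the assumed absorption rate and the linear trapezoid. The endpoint is exploratory, with no hypothesis test and no acceptance limits for the slope. Severity is minor. A conclusion that the plan will report more than proportional exposure would go beyond what the documents show.

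**What to change.** In SAP 7.4.5, replace dose-normalised AUC_t by AUCtau (0-24 h) on Days 25 and 39, for both analytes. State that AUCtau is unnormalised if a slope of 1 is kept as the reference; a dose-normalised AUCtau would need a reference of 0.

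Add one rule for a profile whose last quantifiable sample falls before 24 h: either complete AUCtau by the same stated method at both doses, or exclude that participant's Day 25 and Day 39 pair from this model.

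The cost is SAP wording, since AUCtau is already calculated. The downside is that a participant whose 24 h value cannot be completed may drop out of this one exploratory analysis, which matters somewhat with about 10 participants.

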
Safety Evaluate the safety and tolerability of repeated-dose administration of ALXN1840 15 mg/day and 30 mg/day in participants with WD
	
Safety parameters:
 
 • Treatment emergent adverse events (TEAEs)/serious adverse events (SAEs) • Clinical laboratory assessments (serum chemistry, hematology, coagulation, and urinalysis) • Physical examinations • Heart rate, intervals (PR, QRS, QT and QTc), and clinically significant electrocardiogram (ECG) findings as determined by triplicate 12-lead ECG • Vital sign assessments (blood pressure and heart rate)

Exploratory Determine dose response of ALXN1840 15 mg/day and 30 mg/day for copper balance in participants with WD
	Assess dose response of ALXN1840 on copper balance focusing on copper balance
Determine the effect of treatment duration on copper balance in participants with WD	Determine the effect of time following initiation of ALXN1840 treatment on copper balance
Assess the effects of ALXN1840 on ceruloplasmin, ceruloplasmin-bound copper LBC profiles in plasma in participants with WD	Ceruloplasmin, ceruloplasmin-bound copper, and LBC: Change in ceruloplasmin at Days 1, 8, 25, 29, 36, and Day 39 compared with predose

Objectives	Endpoints
Assess dose proportionality at steady state of doses of ALXN1840 15 mg/day and 30 mg/day in participants with WD	Based on PK parameters
Assess effects ALXN1840 on copper:molybdenum ratio in plasma at steady state in participants with WD	Measure plasma copper:molybdenum ratios at steady state compared with predose
Assess the effects of repeat-dose ALXN1840 on copper:molybdenum ratio in urine and feces in participants with WD	Mean daily copper:molybdenum ratio in urine and feces at steady state compared with predose baseline

Note: The accumulation period refers to time from initiation of ALXN1840 (Day 1) to expected steady state at Day 10, based on 5 times the half-life of 2 days.

Overall Design

This is a single-arm, open-label, repeat-dose study to evaluate the effects of ALXN1840 administration on copper balance in participants with WD. The safety and tolerability of ALXN1840 in participants with WD will also be assessed. ALXN1840 PK in plasma as measured via total molybdenum and plasma ultrafiltrate (PUF) molybdenum will be determined after repeated dosing along with total molybdenum mass balance at steady state.

Disclosure Statement: This is an open-label, 3-period study with 1 arm.

Number of Participants:

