3. In this study, dosing for ALXN1840 will be initiated at 15 mg once daily for a minimum of 4 weeks, with an increase to 30 mg after 4 weeks, unless there are safety concerns that, in the opinion of the Investigator(s) and/or Alexion, may place participants at undue risk, in which case, patients may remain on the 15 mg/day dose for the duration of the study.	
 • Dose range limit 15 mg every other day to 30 mg/day
4. The dose should be decreased or interrupted if any of the relevant Dose Modification criteria are met (Table 7).	
 • Dose range limit 15 mg every other day to 30 mg/day

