4.2. Scientific Rationale for Study Design

The study is designed as an open-label exploratory study to provide a descriptive assessment of copper balance in participants with WD, the target population for ALXN1840 therapy. The study is being conducted as a repeat-dose study to assess the effect of duration of ALXN1840 treatment and the effects of intra-patient dose increase on copper and molybdenum balance in participants with WD. The intra-patient dose escalation schedule is similar to that employed in the current Phase 3 Study WTX101-301. The similar schedule was chosen to characterize the decoppering effects expected early with treatment. This study is designed to supplement the mechanism of action study in healthy participants (Study ALXN1840-HV-108). While healthy participants are expected to be adequate to assess the mechanism of action of ALXN1840, characterization of copper balance in the WD population will help to understand if there are differences in the magnitude of effect between the 2 populations as this may be important to understand the doses that may support a net neutral versus a net negative copper balance. Limited nonclinical data on copper elimination with tetrathiomolybdate suggested copper excretion may be at least maintained or increased with repeated dosing (refer to the current IB).

Therefore, the duration of the study and multiple collection periods will better characterize the pattern of copper elimination over time. Such information may be helpful in understanding the decoppering and maintenance phases.

As the study involves intensive diet control and sampling, the study is planned to be conducted in a small number of participants with WD who will be admitted to a CRU for 2 inpatient periods. Inpatient Period 1 includes a baseline and initial 15 mg/day collection period during the accumulation phase followed by an Outpatient Period; Inpatient Period 2 with a second collection period to support analysis of copper balance at 15 mg/day steady state and a 30 mg/day accumulation and steady state.

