4. DESCRIPTION OF THE PROTOCOL

[figure not shown]
Study ALXN1840-WD-204 will be conducted as an open-label, repeat-dose study to evaluate the effects of ALXN1840 on copper balance in participants with Wilson Disease (WD).

Treatment-experienced (which includes standard of care therapies or ALXN1840) and treatment-naïve participants are eligible for this study. Eligible patients will be classified into one of two cohorts:

- Cohort 1 (treatment experienced): Patients who have received WD therapy for > 28 days
- Cohort 2 (treatment naïve): Patients who have received WD therapy for ≤ 28 days

Following Screening and enrollment, participants will check-in to the clinical research unit (CRU) on Day -8 for the Run-in Period. The purpose of the Run-in Period is to support diet equilibration (Day -7 through Day -5) and measure pretreatment copper and molybdenum balance (Day -4 through Day -1). Participants will remain on a copper/molybdenum-controlled diet throughout both the Inpatient Period 1 (Day -8 to Day 9) and Inpatient Period 2 (Day 23 to Day 40). The study design schematic is presented in Figure 1. While not in the CRU, participants will be encouraged to adhere to their usual copper-controlled diet.

Figure 1: Study Design Schematic

1. Participants eligible for the study will be enrolled on Day -7 and initiated on a copper- and molybdenum-controlled diet, which will be continued during Treatment Period 1 and Treatment Period 2 when in the CRU, through Day 39.
2. Participants will be admitted to the CRU for Treatment Period 1 on Day -8 and may be discharged on Day 9 or remain in the CRU for their own safety or to maintain the integrity of the conduct of the study. Participants who are discharged will be re-admitted on Day 22 or Day 23 for Treatment Period 2 and will remain in house until Day 40. To ensure flexibility, the Outpatient Period may be extended up to an additional 14 days with Investigator approval. In this situation, participants will be given additional study drug to support daily dosing throughout the Outpatient Period. In such cases, the actual Outpatient Period duration will be recorded and the participant will continue Inpatient Period 2 at Day 23.
3. Participants will be administered ALXN1840 at a dose of 15 mg/day on Day 1 through Day 28 and then increase to 30 mg/day on Day 29 through Day 39.
4. Participants will have 3 intake and output collection periods including:
 - Baseline Day -4 through Day -1

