9. APPENDICES

9.1. Sample Size, Power, and Randomization

The sample size will be approximately 10 participants which will allow a general characterization of copper balance in response to ALXN1840.

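### The dose-proportionality power model has no participant term although its two doses come from the same people, so the 90% CI for the slope is mis-sized, and too wide unless within-participant correlation is very low

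*SAP*

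**What the plan says.** SAP 7.4.5 sets out the power model in full: the log PK parameter equals an intercept mu plus a slope beta times log dose. On the right-hand side it says only that "log (dose) will be included as a fixed effect in the power model". The data are defined by "The following PK parameters obtained on Days 25 and 39 will be assessed for dose proportionality", and beta, "along with its 90% CI, will be provided". No participant term, random effect or covariance structure appears there. SAP 9.3, which is reserved for further statistical detail, is marked not applicable. The SAP's abbreviation list includes a mixed model for repeated measures, but no analysis section uses one. An ANOVA is to be explored as well, with no terms stated.

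The design makes the two days a pair. Protocol 1.1 states: "This is an open-label, 3-period study with 1 arm". According to SAP 4, participants are dosed "at a dose of 15 mg/day on Day 1 through Day 28 and then increase to 30 mg/day on Day 29 through Day 39". Protocol 4.2 gives as part of the rationale "the effects of intra-patient dose increase on copper and molybdenum balance in participants with WD". SAP 9.1 adds that "The sample size will be approximately 10 participants". Not every pair need be complete: under Table 4 in Protocol 4.1, if there are safety concerns, "patients may remain on the 15 mg/day dose for the duration of the study".

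**The concern.** Fitted as written, the model leaves all stable differences between participants in the residual. The standard error of the slope is then that of two independent groups of about 10, although each person serves as their own control. If a participant with high exposure at 15 mg/day also tends to have high exposure at 30 mg/day, the interval is wider than the data warrant and covers more often than its nominal 90%.

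Dose proportionality at steady state is a named exploratory objective (Protocol 3, SAP 5.1.3), and this is the only interval specified for the slope. The two doses differ by a factor of only 2, so precision on the slope is limited from the outset. An inflated interval could fail to show a real departure from proportionality that the paired data would reveal.

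**Working it through.** **Inputs from the documents.** Doses 15 and 30 mg/day, so the log-dose spread is ln 2 = 0.693. About 10 participants, taken as n = 10 complete pairs. Two-sided 90% CI.

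**Inputs not in the documents (assumed).** The within-participant correlation rho of the log parameter between Days 25 and 39, range 0 to 0.9, and the CVs. Equal variance s² on both days is also assumed. The SAP states no expected width or precision target, so it has no figure of its own to reproduce.

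**Point estimate.** With two dose levels and complete pairs, beta-hat = mean(log Y on Day 39 − log Y on Day 25) / ln 2, with or without a participant term. Only the interval differs.

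**Half-widths.**
- As written: t(0.95; 2n−2) × s × √(2/n) / ln 2, with t(18) = 1.734.
- With a participant term: t(0.95; n−1) × s × √(2(1−rho)/n) / ln 2, with t(9) = 1.833.

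**Ratio, as written to paired.** (1.734/1.833) / √(1−rho) = 0.946 / √(1−rho). The SD cancels. The ratio equals 1 at rho = 1 − 0.946² = 0.105. Coverage of the two nominal 90% intervals was simulated with 20,000 trials per rho, n = 10 and total CV 40%.

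| Assumed rho | Width ratio | Coverage as written | Coverage paired |
|---|---|---|---|
| 0 | 0.95 | 89.9% | 90.1% |
| 0.3 | 1.13 | 94.6% | 90.0% |
| 0.5 | 1.34 | 97.4% | 90.1% |
| 0.776 | 2.00 | 99.7% | 90.2% |
| 0.9 | 2.99 | above 99.9% | 90.0% |

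**Half-widths on the slope scale.** Take between-participant CV 30–50% and within-participant CV 15–20% (both assumed), with variance = ln(1+CV²) and rho = between variance / total variance. Worked case, 40%/20%: between 0.1484, within 0.0392, total 0.1876, rho 0.79. As written: 1.734 × √(2 × 0.1876/10) / 0.693 = 0.48. Paired: 1.833 × √(2 × 0.0392/10) / 0.693 = 0.23.

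| CV between / within | Implied rho | As written | Paired | Ratio |
|---|---|---|---|---|
| 30% / 20% | 0.69 | 0.40 | 0.23 | 1.7 |
| 30% / 15% | 0.79 | 0.37 | 0.18 | 2.1 |
| 40% / 20% | 0.79 | 0.48 | 0.23 | 2.1 |
| 40% / 15% | 0.87 | 0.46 | 0.18 | 2.6 |
| 50% / 20% | 0.85 | 0.57 | 0.23 | 2.5 |
| 50% / 15% | 0.91 | 0.55 | 0.18 | 3.1 |

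Over this grid the half-width is 0.37–0.57 as written against 0.18–0.23 paired, a ratio of 1.7 to 3.1. These CV choices all imply a high rho. At rho 0.5 the ratio is only 1.34.

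**Incomplete pairs.** A participant kept on 15 mg/day contributes no 30 mg/day value. The slope as written then compares partly different people at the two doses, so beta-hat itself can differ between the two models.

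**Which response.** SAP 7.4.5 names the dose-normalized Cmax and AUCt but takes beta = 1 as proportionality. Since log(Y/dose) = log Y − log dose, normalizing lowers the slope by exactly 1, and proportionality becomes beta = 0. The CI width is unchanged, but the reference value it is read against is not.

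**The case against.** The strongest reply is that little depends on this interval. The study is descriptive, SAP 7.2.1.4 rules out formal testing, and SAP 7.4.5 sets no acceptance limits for the slope and makes the analysis conditional on the data permitting it. With complete pairs the estimate is the same, and above rho of about 0.1 the error is conservative. Proportionality is also assessed graphically, and individual PK parameters are listed (SAP 7.4.3), so the paired ratios can be recovered. Calling log dose a fixed effect may hint at an intended mixed model.

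Most of this stands and limits the importance of the point. It does not remove it. No random effect is written anywhere, and an interval labelled 90% that covers 97% or more under moderate correlation is not what the label says.

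Three stronger readings are tempting but unsupported:
- A reader might infer that the interval is about twice too wide. That needs rho near 0.78, and the documents give neither a correlation nor a CV from which to derive one.
- A reader might infer that almost any result would look compatible with proportionality. Even a half-width of 0.37 to 0.57 excludes proportionality when the estimate lies further than that from its reference value.
- A reader might infer that adding the term is free. It halves the error degrees of freedom, and with incomplete pairs fixed and random participant effects treat the unpaired values differently.

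**Conclusion.** The point holds as an error in a stated model, not merely as missing detail. Followed literally, SAP 7.4.5 analyses paired data as independent and mis-sizes the 90% CI for beta. At n = 10 the interval is too wide once rho exceeds about 0.1 and marginally narrower than the paired one below that. That there is an error follows from the documents; how large it is rests on the assumed rho, equal variances and complete pairs. The affected result is one exploratory objective. The primary copper-balance analysis and the safety analyses are untouched.

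**What to change.** In SAP 7.4.5, state the model as log(parameter) = mu + beta × log(dose) + random participant intercept + error, with the 90% CI for beta taken from within-participant error. Use the same participant term in the exploratory ANOVA. Say how participants without a 30 mg/day value enter the model.

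In the same edit, name the response: the non-normalized Cmax and AUC if beta = 1 stays as the reference, or beta = 0 if the dose-normalized parameters are kept.

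The cost is a few lines of SAP text and one model term. Error degrees of freedom fall from 18 to 9, so if rho is near 0 the interval is about 5% wider (1.833/1.734 = 1.057 by formula; mean half-widths 0.443/0.424 = 1.045 in simulation). The term does not separate dose from time on treatment, because everyone receives 15 mg/day before any increase to 30 mg/day. That limitation should be stated beside the result.
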